Patients who will be undergoing urinary stent insertion during the management of renal or ureteral stones, or other conditions requiring endoscopy will be randomized into the combination or monotherapy arm, based on a computer generated randomization scheme, and will be enrolled into the study arm in a blinded manner. The study is intended to be double-blinded. The drug kit will be linked to the randomization number and both the investigator and patient will thus be blinded to the treatment. All patients will be required to provide a signed informed consent, which outlines the differences in the two treatment arms and study objectives. Patients will be provided the corresponding pills in pre-filled vials, based on their group assignment. Initially, the study used a 7-day treatment regimen. Patients in the monotherapy arm were given a set of Tamsulosin and placebo pills, while the combination therapy arm were given a set of Tamsulosin and Tolderodine ER, with sufficient quantities for 7 days. Pill counts were obtained at the end of the follow-up period to ensure compliance. All patients enrolled into the study were asked to complete the USSQ prior to stent insertion to serve as a baseline assessment of urinary symptoms, and again at 24 hours, 5 days after stent insertion and post stent removal. In the 7-day regimen, 80 patients were enrolled and completed the study (15 patients enrolled but withdrawn, 95 patients in total).

University of Wisconsin-Madison

Study #: 2017-0755

IRB Approval Date: 7/17/2017

The data analysis shows no benefit from being on combination therapy likely secondary to the short duration of therapy.

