In 2014, a change of protocol was approved that extended the study treatment to 21 days. Patients will start the study medication 2 weeks prior to their surgery date and continue for the 1 week duration of the stent. Patients in the monotherapy arm will be given a set of Tamsulosin and placebo pills, while the combination therapy arm will be given a set of Tamsulosin and Tolderodine ER, with sufficient quantities for 21 days. Pill counts will be obtained at the end of the follow-up period to ensure compliance. All patients enrolled into the study will complete the USSQ at baseline prior to starting medication to serve as a baseline assessment of urinary symptoms, prior to stent insertion, and again at 24 hours, 5 days after stent insertion and post stent removal. The patients will have the stent removed in 7 days, which will conclude the study period. If the stent needs to be removed sooner, it will be arranged as per current protocol. Early termination is only relevant if the 5 day USSQ is not completed. In the 21-day regimen, 106 patients are planned to be enrolled. Thus, a total of 201 patients, to see if there is a difference with the longer duration of medication treatment. Subjects have been enrolled on this 21-day regimen since 10/29/2014, and all new subjects use this regimen.

STUDY POPULATION

The key participants of this study will be male and female adult patients with kidney or ureteral stones, or other conditions, requiring unilateral or bilateral ureteral stent placement, either before or after a surgical intervention. Specifically, the post-operative

University of Wisconsin-Madison

Study #: 2017-0755

IRB Approval Date: 7/17/2017

stent patients will include those who have undergone ureteroscopy, percutaneous nephrolithomy or extracorporeal shock-wave lithotripsy.

INCLUSION CRITERIA

Patients with unilateral or bilateral ureteral stent placement for urolithiasis are candidates for enrollment. These include: patients who have undergone ureteroscopy for renal or ureteral calculi, percutaneous nephrolithotomy (PCNL), shock-wave lithotripsy (SWL), or other conditions requiring stent placement post operatively, or for relief of pain or obstruction.

EXCLUSION CRITERIA

Candidates will be excluded from the study if ANY of the following apply:

1. Pre-existing LUTS
2. Active UTI
3. Contraindication to anticholinergic medication
 - a. Prior hypersensitivity or allergy to tolterodine

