In 2014, a change of protocol was approved that extended the study treatment to 21 days. Our sample size calculation in the 21-day regimen was based on the recommended sample size calculations by the original developers of the USSQ ¹. The authors' calculations were based on the results of their validation studies that compared mean domain score and standard deviation differences between stented and control patients, using a 2-tailed test ($p < 0.05$). The percentage change (15%) translates to an absolute change in score by 4 points. Additionally, we extrapolated data from a recent meta-analysis evaluating the efficacy of tamsulosin to relieve stent related symptoms, which showed a mean standard deviation of 6.5 points between the tamsulosin and placebo arm ⁴ to confirm the previous authors' sample size. With an expected decrease of 4 points with the combination therapy, and an assumption of similar standard deviation (6.5), a two-tailed t-test ($p = 0.05$) and power of 0.80, our calculation yielded 43 patients per arm. Given the relatively similar numbers from the two calculations, we opted to use the more conservative sample size of 53 patients per arm as the data collection endpoint.

We are assessing for both an absolute and relative change in the USSQ scores.

1. We will be assessing for a relative change of 4 actual points (which translates to a 15% change, as per Joshi et al's validation study) within each group from immediately post stent insertion at 24 hours compared to day 5.
2. We will also assess for a change in scores between groups, i.e. comparing the mean intra-group score change as described in 1 (i.e., immediately post stent insertion at 24 hours compared to day 5).

University of Wisconsin-Madison
Study #: 2017-0755
IRB Approval Date: 7/17/2017

The questionnaire responses will be analyzed using cross tabulations and descriptive statistics to assess differences between groups. Paired *t*-tests will be used to assess within-group change in scores from the USSQ (comparison between post-op, i.e. at 48 hours, and day 5) and other discriminant properties. *T*-tests will be used to assess inter-group score changes.

The intent-to-treat principle will be employed in the event subjects have to withdraw from their assigned group, although this is not expected given that both treatment medications are used extensively in urology, and both treatment regimens are occasionally employed based on anecdotal physician experience.

DATA SECURITY:

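### The paired test uses a 48-hour USSQ that is never collected, item 1 puts a between-arm threshold on each arm's own change, and item 2's 24-hour reference can subtract early benefit

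*Combined protocol and SAP*

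**What the plan says.** **Time point.** Under STATISTICAL ANALYSIS & POWER CALCULATIONS, the paired t-tests of within-group change are defined as a "comparison between post-op, i.e. at 48 hours, and day 5". The forms collected are listed under STUDY ACTIVITIES. In the 7-day regimen patients "were asked to complete the USSQ prior to stent insertion to serve as a baseline assessment of urinary symptoms, and again at 24 hours", then at day 5 and after stent removal. In the 21-day regimen they complete the USSQ before starting medication, then "prior to stent insertion, and again at 24 hours, 5 days after stent insertion and post stent removal".

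**Threshold.** Item 1 of the analysis section reads "We will be assessing for a relative change of 4 actual points", equated there with 15%, "within each group from immediately post stent insertion at 24 hours compared to day 5". OBJECTIVES AND HYPOTHESIS describes the same 15% as a further fall in the experimental group relative to control, and states the measure as a mean difference in the USSQ urinary symptom index. The sample size uses 4 points, SD 6.5, a two-tailed t-test at 0.05 and power 0.80, giving 43 per arm; 53 per arm is adopted.

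**Between-arm test.** Item 2 reads "We will also assess for a change in scores between groups, i.e. comparing the mean intra-group score change as described in 1", again from 24 hours to day 5. A later sentence says that t-tests "will be used to assess inter-group score changes".

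**Treatment start.** In the 21-day regimen, study drug starts two weeks before surgery.

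**The concern.** The paired-test sentence cannot be carried out as written, because it needs a form that no patient completes, and it conflicts with items 1 and 2.

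The same 4 points also stands for two different quantities. A change within one arm includes the course common to both arms after stent insertion, as well as any drug effect. The trial's question is what tolterodine adds to tamsulosin, and only a contrast between arms answers that. A report that set each arm's change beside 4 points, or compared two paired p-values, could credit or deny tolterodine an effect for reasons unrelated to it.

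Correcting 48 to 24 hours leaves a further problem. In the 21-day regimen the 24-hour score is taken on treatment. A change measured from it removes any benefit already present, which is the benefit that the pre-treatment hypothesis predicts.

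**Working it through.** **1. Forms collected against forms analysed**

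| Source | Post-insertion USSQ times |
|---|---|
| STUDY ACTIVITIES, 7-day regimen | 24 hours, day 5, after removal |
| STUDY ACTIVITIES, 21-day regimen | 24 hours, day 5, after removal |
| Analysis items 1 and 2 | 24 hours, day 5 |
| Paired-test sentence | 48 hours, day 5 |

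Only the last row lacks a matching form.

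**2. Which quantity the 4 points is**

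Inputs from the analysis section: difference 4, SD 6.5, two-sided 0.05, power 0.80.

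- Two-sample, normal approximation: n per arm = 2 × [6.5 × (1.960 + 0.842)/4]² = 41.5, so 42.
- Two-sample t-test (noncentral t): 42.4, so 43 per arm. This is the plan's figure.
- Paired t-test, taking 6.5 as the SD of change: 22.7, so 23.

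The stated 43 is therefore a between-arm figure, in agreement with the objectives. The 53 comes from a cited source whose inputs are not given and cannot be reproduced.

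**3. What two paired tests show when the arms are identical**

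The documents do not say whether 6.5 is the SD of a single score or of a change. If it is a single-score SD, the SD of change is 6.5 × √(2(1 − r)), where r is the correlation between the two scores. Assuming r = 0.7, 0.5 and 0.3 gives 5.03, 6.5 and 7.69.

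Suppose both arms truly fall by 2 points, with 53 per arm. Let p be the power of one paired t-test. The probability that exactly one of the two tests is significant is 2p(1 − p).

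| SD of change | p | 2p(1 − p) |
|---|---|---|
| 5.03 | 0.81 | 0.31 |
| 6.5 | 0.594 | 0.48 |
| 7.69 | 0.46 | 0.50 |

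**4. What item 2 detects**

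Let f be the share of a 4-point day-5 benefit already present at 24 hours (an assumption). The expected between-arm difference in change is 4 × (1 − f). Power of the two-sample t-test at 53 per arm:

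| f | Expected difference | SD 5.03 | SD 6.5 | SD 7.69 |
|---|---|---|---|---|
| 0 | 4 | 0.98 | 0.88 | 0.76 |
| 0.5 | 2 | 0.53 | 0.35 | 0.26 |
| 1 | 0 | 0.05 | 0.05 | 0.05 |

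At f = 0.5 and SD 6.5, 80% power would need 166 per arm (normal approximation).

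**5. Precision of a between-arm difference**

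The 95% CI half-width is t(0.975, 104) × SD × √(2/53) = 1.983 × SD × 0.1943. This is 2.5 points at SD 6.5, 1.9 at 5.03 and 3.0 at 7.69.

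**The case against.** **The 48 hours is a slip that corrects itself.** Both schedules and both numbered items say 24 hours, and no 48-hour data would exist to analyse. That stands as to weight, but the sentence still has to be corrected.

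**Item 1 states no decision rule.** It gives no pass/fail criterion, and the plan nowhere says that within-arm change is evidence of efficacy. This stands. The working therefore examines the paired t-test that the plan names, and does not ask how often an arm's mean would cross 4 points.

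**Four points may also be meaningful within an arm.** Item 1 attributes it to the validation study, and using one benchmark twice is not in itself a contradiction. The documents neither establish nor exclude this. A within-arm benchmark could be kept if it were justified separately. It would still not measure tolterodine's added effect.

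**Two stronger readings are tempting.** A reader might infer that the plan compares the arms only through separate paired tests. It does not: item 2 and the t-test sentence plan a between-arm comparison. A reader might also infer that item 2 is invalid. The documents do not support that either. It is a randomised comparison and keeps its type I error if treatment has no effect at any time. Its weakness is what it can miss, and it applies to the 21-day regimen. For the 7-day regimen the documents do not say when the first dose fell relative to the 24-hour form.

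**Conclusion.** Two points are wrong as written: the 48-hour reference, and the placing of a between-arm threshold on within-arm change. Both rest on the current text and on the reproduced 43 per arm, not on assumptions.

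Paired results cannot stand in for the comparison of arms. With identical 2-point falls they disagree in about 48% of trials (31% to 50% over the assumed SD range).

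Item 2 is the right kind of test, but its adequacy is conditional. The 88% power requires that none of the benefit is present at 24 hours, that the SD of change is 6.5, and that all 53 per arm are analysed. If the 7-day withdrawal rate (15 of 95) recurred and only completers had scores, 53 × 80/95 = 44.6 per arm would remain, with power of 81% to 82%. A null result on item 2 would not by itself mean no benefit. The shares present at 24 hours and the correlations are assumptions, since the documents give neither.

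This should be corrected. It does not invalidate the trial.

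**What to change.** Before the 21-day data are analysed, amend the analysis section as follows:

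1. In the paired-test sentence, replace 48 hours with the collected 24-hour time point.
2. Remove the 4 points from item 1 and attach it to the between-arm difference in the USSQ urinary symptom index, reported with its 95% CI.
3. Label the within-arm paired tests descriptive. Justify any within-arm benchmark separately.
4. Answer the stated objective with a between-arm comparison of the day-5 urinary index, adjusted for the pre-medication USSQ score. The 21-day schedule already collects that score and the analysis section does not use it. Keep the 24-hour-to-day-5 change as a secondary analysis.

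The cost is a few sentences and slightly more analysis work, with no new forms and no change to the planned 53 per arm. If the SD of the analysed quantity were 7.69, 53 per arm would give 76% power for 4 points and 80% would need about 59 per arm. The SD used should therefore be stated for the quantity actually analysed.

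### The only between-arm test is an unadjusted t-test on the 24-hour to day-5 change: it needs both forms and leaves the collected pre-drug USSQ unused, a modest loss that is cheap to remedy

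*Combined protocol and SAP*

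**What the plan says.** Statistical Analysis & Power Calculations, item 2, sets the between-arm comparison as "comparing the mean intra-group score change as described in 1 (i.e., immediately post stent insertion at 24 hours compared to day 5"). The paragraph after it names the test: t-tests "will be used to assess inter-group score changes". No covariate, repeated-measures model, imputation method or rule for a missing form appears. The same paragraph starts the within-group change at a different time, "comparison between post-op, i.e. at 48 hours, and day 5", although the 21-day schedule has no 48-hour form.

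Under Study Activities, patients on the 21-day regimen "complete the USSQ at baseline prior to starting medication to serve as a baseline assessment of urinary symptoms, prior to stent insertion". Those are the two forms before the stent. The questionnaire is then repeated "again at 24 hours, 5 days after stent insertion and post stent removal", which gives two forms while the stent is in place and one afterwards. The same paragraph adds: "Early termination is only relevant if the 5 day USSQ is not completed".

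The sample size rests on a 4-point difference, an SD of 6.5, two-sided 0.05 and power 0.80. This gives 43 per arm. The plan adopts 53 per arm and plans to enrol 106.

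**The concern.** A change score exists only for a patient who returned both forms. The 24-hour form falls on the day after surgery, so some forms may be missing even where the day-5 form was completed. With no rule for that case, a t-test on changes has nothing to enter for such a patient, and a randomised patient with a usable day-5 outcome drops out of the only between-arm test.

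The plan also gathers a true pre-treatment baseline and then leaves it out of that test. Adjusting for a pre-randomised-treatment score costs nothing in data collection and, for a day-5 comparison, can only help to the extent that the two scores are correlated. At stake are some precision and the inclusion of all patients with outcome data. No figure in the plan is thereby wrong.

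**Working it through.** **Inputs from the plan.** Difference 4 points, SD 6.5, two-sided alpha 0.05, power 0.80, 43 per arm calculated, 53 per arm adopted.

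**Assumed, because the documents give no values.**
- Correlation ρ between pre-drug and day-5 scores: 0.2, 0.3, 0.5.
- Correlation r between 24-hour and day-5 scores: 0.3, 0.5, 0.7.
- Share m of missing 24-hour forms: 10% or 20%.

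**1. The plan's own figure.** The standardised difference is 4/6.5 = 0.615. A two-sample t-test at 80% power needs 42.4 per arm, rounded up to 43, which matches. At 53 per arm, power is 0.881. This holds if 6.5 is the SD of the variable analysed. The plan does not say whether 6.5 describes a single score or a change.

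**2. Planned change, 24-hour forms missing, complete pairs only.** Pairs per arm = 53(1 − m).
- m = 10%: 47.7 pairs, power 0.845 (0.839 at 47).
- m = 20%: 42.4 pairs, power 0.800 (0.796 at 42).

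**3. Planned change, mixed model without the pre-drug score.** Suppose every day-5 score is present, variances are equal, and the SD of the change is held at 6.5. The variance of the estimated mean change, relative to full data, is then

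F = [(1 − r) + (1 + r)/(1 − m)] / 2, and effective n = 53/F.

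At m = 20%:

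| r | F | Effective n per arm | Share of the 10.6 lost patients recovered | Power |
|---|---|---|---|---|
| 0.3 | (0.7 + 1.625)/2 = 1.1625 | 45.6 | 30% | 0.83 |
| 0.5 | (0.5 + 1.875)/2 = 1.1875 | 44.6 | 21% | 0.82 |
| 0.7 | (0.3 + 2.125)/2 = 1.2125 | 43.7 | 12% | 0.81 |

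A day-5 score alone says little about a change, so the model recovers little for this contrast.

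**4. Day-5 contrast adjusted for the pre-drug score.** The standard error is multiplied by √(1 − ρ²), and the equivalent unadjusted n is 53/(1 − ρ²). A missing 24-hour form does not enter.

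| ρ | √(1 − ρ²) | Cut in standard error | Equivalent n per arm | Power at 53 (SD 6.5 for day 5) |
|---|---|---|---|---|
| 0 | 1 | 0% | 53 | 0.881 |
| 0.2 | 0.980 | 2% | 55 | 0.893 |
| 0.3 | 0.954 | 5% | 58 | 0.908 |
| 0.5 | 0.866 | 13% | 71 | 0.952 |

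Pre-existing LUTS is an exclusion, which narrows the spread of baseline scores, so the low end is plausible.

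**5. Is a change score noisier in itself?** If 6.5 is the SD of a single score, the SD of the change is 6.5√(2(1 − r)): 7.69, 6.50 and 5.03 at r = 0.3, 0.5 and 0.7. The change is noisier than the raw day-5 score only when r is below 0.5.

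**The case against.** The strongest objection is that the two halves of the point bear on different contrasts. Missing 24-hour forms hurt the planned change but not a day-5 comparison. The 2%, 5% or 13% gain belongs to a day-5 comparison and not to the planned change. A reader might infer that the planned test has a larger standard error than it need have by those percentages. The documents do not support that, and step 5 shows that the change can even have the smaller SD. This part of the objection stands. It is why the choice of contrast matters more than the choice between a t-test and a mixed model.

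Four other stronger readings also go beyond the text:

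- **That patients are known to be dropped.** No missing 24-hour form is reported, and no sentence says such patients are removed. The loss follows from a change-score test with no missing-form rule. The Safety and Monitoring section also schedules regular checks on questionnaire completion, which should limit it.
- **That a day-5 form alone makes a patient complete and counts toward the 53.** The sentence "Early termination is only relevant if the 5 day USSQ is not completed" comes directly after one about removing the stent early and may concern only that. The data collection endpoint is not tied to the day-5 form.
- **That the intent-to-treat statement is broken by skipped forms.** It is written for patients who withdraw from their assigned group. Its clearer tension is with Safety and Monitoring, which excludes patients who have discontinued medication.
- **That the trial becomes underpowered.** With 20% of 24-hour forms missing and no other loss, power is still 0.80, the plan's target. The move from 43 to 53 per arm absorbs it.

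Finally, if the sorest patients skip the 24-hour form, missingness depends on the score that was not seen. That strains the missing-at-random assumption of a mixed model too.

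What survives is that the test as written needs both forms, has no rule when one is missing, and ignores a baseline collected for the purpose.

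**Conclusion.** The point holds as a modest improvement. The only between-arm test is an unadjusted comparison of the 24-hour to day-5 change. It cannot use a patient without a 24-hour form, and it makes no use of the pre-drug or pre-stent USSQ.

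The size depends on the contrast, and every correlation and missing rate is assumed. For the adjusted day-5 difference, the standard error falls by 2% to 13%, most plausibly near the low end, and a missing 24-hour form is harmless. For the planned change, 20% missing takes power from 0.88 to 0.80, and a mixed model without the covariate brings it back only to about 0.81 to 0.83. The number of patients affected is unknown, and the plan's 43 per arm reproduces.

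**What to change.** 1. Analyse the urinary symptom index in all randomised patients with any post-stent score. Use a linear mixed model over 24 hours and day 5, with terms for arm, visit, arm-by-visit, pre-drug index and pre-drug-by-visit, and an unstructured covariance.
2. Name one primary contrast before unblinding. The between-arm difference at day 5, adjusted for the pre-drug score, is where the gain arises. An ANCOVA of the day-5 score on the pre-drug score would serve equally for that contrast. Report the estimate with its 95% confidence interval.
3. Keep the t-test on the 24-hour to day-5 change as a sensitivity analysis.
4. State the rule for a missing form, and report missing 24-hour and day-5 forms by arm.
5. Reconcile 24 with 48 hours as the start of the change, say which variable the SD of 6.5 describes, and reconcile the intent-to-treat statement with the exclusion of patients who discontinue medication.

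The cost is SAP wording and a little more programming, with no new visits, forms or patients. The downside is reliance on missing-at-random, which may be strained if the sorest patients skip the 24-hour form. The model also cannot help patients with no post-stent score at all.
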